11.1.4 Device Deficiencies

Device Deficiencies means any inadequacy of a medical device with respect to its identity, quality, durability, reliability, safety or performance

11.2 Documentation

11.2.1 (Serious) Adverse Events / Adverse Device Effects

Independent from a possible relation to the investigational device, every AE spontaneously reported by the subject or observed by the investigator will be reported on the appropriate page of the case report form. Furthermore, the investigator shall actively ask the subject about the occurrence of any (S)AE at each visit and note any abnormal laboratory findings. For each adverse event the following information shall be documented:

- Description of the event (diagnosis and symptoms in verbatim terms). For the most common ERCP-related adverse events the following terms could be selected:
 - Pancreatitis
 - Cholangitis
 - Cholecystitis
 - Bleeding
 - Perforation (according (Stapfer 2000)
 - Type I Duodenal wall perforation (by the endoscope)
 - Type II Periampullary perforation (by sphincterotomy/ precut)
 - Type III Biliary or pancreatic duct perforation (by intraductal instrumentation)
 - Type IV Retroperitoneal gas alone
 - Sedation-related AEs
- Outcome,
- Seriousness,
- Duration (start date and stop date),
- Causal relationship to the investigational device.
Causality assessment will be done by the investigator using a 5-category system (no related / unlikely / possible / probable / causal relationship).
- Any therapy or corrective action initiated including.

The results of any complementary tests performed (laboratory tests, ECG, etc.) must be pseudonymized by the investigator prior to forwarding information to the sponsor. A period of 4 weeks for follow up of AEs after the subject has routinely completed or prematurely terminated the study seems sufficient. This means that any additional information needed to assess the (S)AE should be collected and documented in the respective CRF within one month after occurrence.

Clinical Investigation Plan

CIP Reference No.:2018-GI (OEKG) -01. The **SAMISEN** study - Final Version 03 - Date 28-Jun-2021

11.2.2 Device deficiencies

Two device deficiencies of the disposable Spiral Segment were documented in previous clinical studies with PowerSpiral. The technical issues are addressed and solved.

11.3 Reporting Responsibilities

11.3.1 Serious Adverse Events (SAE) / Serious Adverse Device Effects (SADE)

After the signature on the consent form is obtained, any SAE occurring while the subject is enrolled in the study must be immediately reported by the investigator.

11.3.1.1 Serious Adverse Event - Initial Report

The investigator has to report every SAE immediately after he/she becomes aware of the SAE.

The Sponsor compile an accumulated SAE list and share with Ethical Committees on a bi-annual basis (if requested by the respective Ethical Committees). However, for international safety reporting requirements the sponsor needs to be informed immediately about any observed SAE.

11.3.1.2 Serious Adverse Event - Follow-up Report

If the event / SAE is not resolved further information (e.g. laboratory reports, surgical reports) for full assessment is needed and shall be provided as soon as it becomes available. The sponsor may request additional documents, shall be provided within 5 days.

11.3.2 Device deficiencies

Device deficiencies shall be reported to the sponsor not later than 7 working days after observation.

11.4 Anticipated Adverse Events

Foreseeable risks include those typically associated with ERCP performed under general anesthesia or sedation.

The following device and process related events were observed in previous Investigator-Initiated-Trials with PowerSpiral and reported in the context of post-market surveillance. The SAMISEN study will contribute and extend the safety profile of the PowerSpiral device.

Clinical Investigation Plan

CIP Reference No.:2018-GI (OEKG) -01. The SAMISEN study - Final Version 03 - Date 28-Jun-2021

Table 2 List of anticipated (Serious) Adverse Events

- tissue damage
- mucosal damage
- laceration
- inflammation
- bleeding
- hematoma
- perforation
- penetration
- infection
- pain (such as abdominal pain sore throat and odynophagia)
- abdominal distention
- discomfort (such as abdominal discomfort and swallowing discomfort)
- indigestion
- nausea
- vomiting
- cardiovascular problem (bradycardia, tachycardia, hypotension and hypertension)
- dysphagia
- respiratory system disorder (such as aspiration pneumonia, cough, hypoxemia, respiratory instability and mediastinal emphysema)
- pancreatitis
- fever
- hyperamylasemia
- hyperlipasemia
- intestinal obstruction
- intestinal necrosis
- intussusception
- parotitis
- hiccup
- electrical shock
- burn (operator)
- physical deconditioning
- distress
- allergy
- heat injury
- exposure
- acute pancreatitis
- cholangitis
- aspiration pneumonia
- CO2 narcosis
- atrioventricular block
- surgery (as a result of perforation, laceration, bleeding, tissue damage, etc)
- bruise (Health Care Professional)
- bleeding (Health Care Professional)

Clinical Investigation Plan

CIP Reference No.:2018-GI (OEKG) -01. The **SAMISEN** study - Final Version 03 - Date 28-Jun-2021

11.5 Data Monitoring Committee

Not applicable.

Clinical Investigation Plan

CIP Reference No.:2018-GI (OEKG) -01. The **SAMISEN** study - Final Version 03 - Date 28-Jun-2021

12 VULNERABLE POPULATION

It is not planned to include a vulnerable population.

Clinical Investigation Plan

CIP Reference No.:2018-GI (OEKG) -01. The SAMISEN study - Final Version 03 - Date 28-Jun-2021

13 SUSPENSION OR PREMATURE TERMINATION

Certain circumstances may lead to early termination of an entire clinical investigation, in particular for ethical or safety reasons such as:

- The high frequency and/or unexpected severity of adverse events.
- Unsatisfactory recruitment of subjects as far as their quantity or quality is concerned or recurrent incomplete/inappropriate collection of data.

The decision to put a study on hold or for premature termination will be made by the Sponsor.

Clinical Investigation Plan

CIP Reference No.:2018-GI (OEKG) -01. The **SAMISEN** study - Final Version 03 - Date 28-Jun-2021

14 PUBLICATION POLICY

The sponsor is explicitly committed to publish the trial results in a scientific medical journal and / or presented at scientific meetings. The Investigator agrees that any publication by the Study Site of study results conducted at their study site shall not be made before the first multicenter publication and as agreed between the sponsor and the Coordinating Clinical Investigator.

For greater certainty, it is hereby recalled that in its capacity as sponsor of the trial, Olympus Europa SE & Co. KG is solely responsible to co-ordinate the publications of multicenter clinical trials in order to ensure that the related results are reported in a coherent and responsible manner so that results from clinical trial data subsets are not published in advance of or without clear reference to the primary publication and/or do not repeat such primary publication. Olympus Europa SE & Co. KG decides about the nomination of investigators as authors on the basis of its internal policies, requirements of the publishers and generally accepted standards of authorship. Therefore, Olympus Europa SE & Co. KG shall be duly informed of any publication plans in order to review any proposed manuscript before submission for publication.

Clinical Investigation Plan

CIP Reference No.:2018-GI (OEKG) -01. The **SAMISEN** study - Final Version 03 - Date 28-Jun-2021

16 STUDY TIMELINE

Screening period	November 2021 – December 2022
Recruitment period:	November 2021 – December 2022
Database lock	February 2023
Data Review Meeting	February 2023
Statistical analysis:	April 2023
First data available	May 2023
Draft report:	August 2023
Final CIR	September 2023

Clinical Investigation Plan

CIP Reference No.:2018-GI (OEKG) -01. The SAMISEN study - Final Version 03 - Date 28-Jun-2021

17 ANNEX 01: DEEP ENTEROSCOPY PROCEDURE

17.1 General Information

A lack of frequent stalling of the rotation should be interpretive as a warning to assess the patient and scope position.

Continued rotation without advancement should also be seen as maximum insertion depth.

The limit function does not guarantee the safety of the procedure. The operator must judge if safe insertion can be continued on a case-by-case basis.

The LIMIT Function?

The limit function stops the rotation of the single use PowerSpiral tube when the electric current to the motor on the endoscope a setting value. To release, remove your foot from the pedal on foot switch.

17.2 General Insertion tips

Gentle forward pressure is used when rotation is started as well as throughout the procedure.

Minimal CO₂ insufflation is recommended as small bowel distention will decrease spiral advancement.

Irrigation using a water jet may help with lumen visualization and spiral advancement. Intermittent external abdominal compression is often helpful to facilitate engagement and advancement of the spiral segment.

17.3 General Withdrawal tips

Insufflation may be used at will at this time.

Although the scope may seem to be moving out of the patient quickly, it is important to keep holding the scope firmly.

Slow controlled withdrawal is the key. This is accomplished by backward rotation while maintaining the scope position and keeping the tip in motion

[figure not shown]
Clinical Investigation Plan

CIP Reference No.:2018-GI (OEKG) -01. The SAMISEN study - Final Version 03 - Date 28-Jun-2021

17.4.2 Passing through the Pharynx & Esophagus

[figure not shown]
The spiral segment is engaged in the upper esophageal sphincter and rotational advancement is continued using the forward foot switch.

The patient's neck is extended as needed to straighten the passage through the cervical esophagus as the rotating spiral section is less flexible than the remaining section of the scope.

Once the spiral section is past the cervical esophagus, the patient's neck no longer needs to be extended and may be returned to the usual position

Note

Gentle forward pressure is applied while the spiral segment is rotated slowly and intermittently using the foot switch facilitating intubation of the esophagus.

[figure not shown]
A decrease in the amount of resistance and torque required for advancement is an indicator that the cervical esophagus has been passed.

Clinical Investigation Plan

[figure not shown]
CIP Reference No.:2018-GI (OEKG) -01. The **SAMISEN** study - Final Version 03 - Date 28-Jun-2021

17.4.3 Passing through the Stomach

Upon entering the stomach, gastric contents should be aspirated and CO₂ insufflation should be kept to minimum.

While on the stomach, gentle pushing with rotation of the spiral segment is recommended for advancement.

When the insertion tube mark at 80cm is in the mouthpiece, the entire spiral segment is in the stomach.

Clinical Investigation Plan

CIP Reference No.:2018-GI (OEKG) -01. The **SAMISEN** study - Final Version 03 - Date 28-Jun-2021

17.4.4 Passing through the Duodenum

[figure not shown]
The duodenum and proximal jejunum are fixed. Passage through the segment is accomplished with forward rotation and gentle advancement of the scope.

Avoid prolonged rotation when the spiral segment is in the second portion of the duodenum.

Looping should be avoided but can be managed careful withdrawal of the scope along with forward rotation of the spiral segment.

[figure not shown]
Fluoroscopy or ScopeGuide may be useful in assessing looping.

Clinical Investigation Plan

CIP Reference No.:2018-GI (OEKG) -01. The **SAMISEN** study - Final Version 03 - Date 28-Jun-2021

17.4.5 Passing through the Small Bowel Distal to the Ligament of Treitz

[figure not shown]
Once the spiral segment is positioned in the proximal jejunum, advancement is accomplished primarily by rotation of the spiral segment.

Intermittent gentle advancement of the scope in 3-5cm increments when progress seems to slow down visually.

Insert as if drawing concentric circles.

Clinical Investigation Plan

CIP Reference No.:2018-GI (OEKG) -01. The **SAMISEN** study - Final Version 03 - Date 28-Jun-2021

17.4.6 Reaching the Terminal Ileum

The following images will provide indication of the scope being close to the terminal ileum.

[figure not shown]
The ileum becomes apparent with less prominent villi and prominent lymphoid follicles.

The procedure should be terminated if the cecum is encountered.

Do not pass the spiral through the ileo-cecal valve. Stop forward advancement.

[figure not shown]

Clinical Investigation Plan

CIP Reference No.:2018-GI (OEKG) -01. The **SAMISEN** study - Final Version 03 - Date 28-Jun-2021

17.4.7 Withdrawal Techniques

Gentle forward pressure should be maintained to facilitate a slow, controlled withdrawal. This is especially true when the duodenum is encountered.

Every effort should be made to be sure the spiral segment is free in the stomach and no longer engaged in the duodenum/ pylorus prior to allowing the spiral segment to engage the lower esophagus sphincter. This is often accomplished by intermittent use of the forward foot switch to confirm disengagement in the stomach. tent use of the forward foot switch to confirm disengagement in the stomach.

[figure not shown]
The PowerSpiral enteroscope has a special marking at 80cm to indicate the spiral segment is approaching the lower esophagus sphincter.

Clinical Investigation Plan

CIP Reference No.:2018-GI (OEKG) -01. The SAMISEN study - Final Version 03 - Date 28-Jun-2021

As the spiral segment encounters the cervical esophagus, the neck is once again extended to facilitate atraumatic withdrawal while the spiral segment is rotating.

Note

Increased resistance is an indicator of remaining pleated bowel on the spiral segment. This requires advancement of the scope holding position and then resuming backward rotation.

[figure not shown]
Clinical Investigation Plan

CIP Reference No.:2018-GI (OEKG) -01. The **SAMISEN** study - Final Version 03 - Date 28-Jun-2021

[figure not shown]
17.5 Retrograde Approach

17.5.1 Passing through the Colon

The spiral enteroscope can be passed through the colon with continuous rotation and gentle pressure.

Forward rotation of the spiral segment should be used for passage through the anal sphincter.

If lumen cannot be visualized, rotate with caution to advance.

CO₂ insufflation should be minimized and water injection should be considered.

[figure not shown]
[figure not shown]
[figure not shown]
Clinical Investigation Plan

CIP Reference No.:2018-GI (OEKG) -01. The SAMISEN study - Final Version 03 - Date 28-Jun-2021

17.5.2 Eliminating a Loop

Eliminate a loop by maintaining position of the spiral segment and withdrawing the scope while applying forward rotation to the spiral segment.

[figure not shown]
[figure not shown]
[figure not shown]
Sigmoid Colon:

Clinical Investigation Plan

CIP Reference No.:2018-GI (OEKG) -01. The SAMISEN study - Final Version 03 - Date 28-Jun-2021

Transverse Colon:

Tips

[figure not shown]
The principal is to minimize the amount of scope inserted in the colon thereby preserving as much scope length as possible with which to examine the small bowel. This is accomplished by minimizing insufflation, and the constant use of withdrawing, torquing, shortening, and pleating techniques.

Clinical Investigation Plan

[figure not shown]
CIP Reference No.:2018-GI (OEKG) -01. The **SAMISEN** study - Final Version 03 - Date 28-Jun-2021

17.5.3 Passing through the Ileo-cecal Valve

The ileocecal valve is intubated using standard colonoscopy techniques.

[figure not shown]

When passing through the ileocecal valve, insertion can be facilitated by decreasing the angle of insertion into the ileum by means of manual compression or postural change.

If insertion into the terminal ileum is still difficult, try retro-flexing the scope inside the cecum and inserting the U-shaped distal end of the scope into the ileum with a push-pull technique.

After passing through the ileocecal valve, advancement is accomplished by rotation of the spiral segment and intermittent advancement of the scope through the rectum as well as intermittent manual compression to facilitate acquisition of the small bowel on to the insertion tube.

[figure not shown]

Clinical Investigation Plan

CIP Reference No.:2018-GI (OEKG) -01. The **SAMISEN** study - Final Version 03 - Date 28-Jun-2021

17.5.4 Passing through the Small Bowel

[figure not shown]
Once the spiral segment is positioned in the terminal ileum, advancement is accomplished primarily by rotation of the spiral segment and intermittent gentle advancement of the scope in 3-5 cm increments when progress seems to slow down visually.

17.5.5 Reaching the Proximal Jejunum

The following images will provide indication of the scope being close to the proximal jejunum.

The procedure should be terminated if the ampulla or duodenal bulb is encountered.

[figure not shown]

Clinical Investigation Plan

[figure not shown]
CIP Reference No.:2018-GI (OEKG) -01. The **SAMISEN** study - Final Version 03 - Date 28-Jun-2021

17.5.6 Withdrawal Techniques

[figure not shown]
Slow withdrawal is accomplished with the foot switch in the reverse position and constant maneuvering of the scope tip to facilitate gradual and controlled release of the intestine off the tip of the scope.

Occasional forward activation of the spiral may be necessary for a slow, controlled withdrawal.

[figure not shown]
Once the cecum is reached, the scope is withdrawn as in a standardized colonoscopy with or without spiral rotation.

Clinical Investigation Plan

CIP Reference No.:2018-GI (OEKG) -01. The SAMISEN study - Final Version 03 - Date 28-Jun-2021

When the anal sphincter is reached, the passage is accomplished by the spiral rotation in the backward direction.

Note

Retroflexion should not be performed with the spiral segment in the patient.

1.1 Protocol Version and Amendments

The statistical analysis plan is based on final version 03 of the study protocol of study SAMISEN dated June 28th, 2021 (CIP#: 2018-GI(OEKG) – 01).

1.2 Applicable Standards

None.

1.3 Review Report

<text>

1.4 Other Documents

[figure not shown]
None.

2 Study Design and Objectives

2.1 Study Design

SAMISEN is an international, multicenter, open label, non-randomized, prospective, observational open-label study. Phase B has an exploratory study design for data collection in ERCP conducted with PowerSpiral.

2.2 Flow chart of study activities

2.3 Study Objectives

The main objective of this registry is to collect data on the safety and performance of the new motorized PowerSpiral device when used as intended by the manufacturer. It is assumed that the new device and its safety profile is non-inferior to preceding generations of balloon assisted enteroscopes.

As clinical performance and efficacy is equally important for the user this study also collects efficacy and handling data of the new device.

2.4 Efficacy Variables

The efficacy parameters are defined as follows:

- **Total success rate:** Defined as the combined percentage of enteroscopy success rate, biliary cannulation success rate and procedural (therapeutic) success rate, i.e., the number of therapeutic successes divided by the number of patients who received an enteroscopy.
- **Enteroscopy success rate:** Defined as the percentage of procedures with the ability to reach the major papilla or the biliary anastomosis, i.e., the number of successful enteroscopies divided by the number of patients who received an enteroscopy.
- **Biliary cannulation success rate:** Defined as the percentage of procedures with the ability to selectively cannulate the bile duct and conduct a cholangiography, i.e., the number of successful cannulations divided by the number of successful enteroscopies.
- **Therapeutic (procedural) success rate:** Defined as the percentage of procedures in which the intended treatment could be successfully completed, i.e., the number of therapeutic successes divided by the number of successful bile cannulations.
- **Total procedure time:** Time from start of oral insertion to final withdrawal of the device.
- **Enteroscopy time:** Time from start of oral insertion to reaching the papilla or the biliary anastomosis.
- **User feedback** and assessment of handling characteristics and other logistical aspects regarding:
 - Handling of PowerSpiral
 - Instrument insertion of PowerSpiral
 - Precision of positioning during therapy of PowerSpiral
 - Time needed for procedure of PowerSpiral
 - Staff and resources needed for procedure of PowerSpiral

2.5 Safety Variables

The following safety variables will be collected:

- Enteroscopy-associated serious adverse events during and after enteroscopy procedure
- ERCP-related serious adverse events (Dumonceau et al., 2020)
- Sedation/anesthesia related serious adverse events
- Other serious adverse events (procedure or product related)
- Adverse events during enteroscopy and ERCP procedure
- Adverse events of interest are: bleeding, mucosal damage and pancreatitis (including hyperamylasemia)

2.6 Coding dictionaries

- Adverse events: IMDRF current version
- Baseline findings: not applicable
- Medical history: not applicable
- Medication: not applicable

3 Statistical Evaluation

3.1 Populations for Analysis

All patients who did not undergo at least one enteroscopy will be considered as dropouts. Dropouts will be excluded from any statistical analyses.

Two different analysis populations will be defined:

The **safety population (SAF)** will consist of all patients who underwent at least one enteroscopy.

The **ITT population (ITT)** will comprise all patients who underwent at least one enteroscopy and did not have any major protocol deviation.

The safety analysis will be performed on the safety population (SAF), which consists of all patients who underwent at least one enteroscopy.

Efficacy analyses will be based on the intent-to-treat (ITT) population, which includes all patients

- who underwent at least one enteroscopy and
- who had not major protocol deviations.

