3.6 Efficacy Analysis

The following efficacy analyses will be performed based on the ITT population:

- The total success rate (the number of therapeutic successes divided by the number of patients who received an enteroscopy) will be computed alongside with its 95% Clopper-Pearson confidence interval.
- The enteroscopy success rate (percentage of procedures with the ability to reach the major papilla or the biliary anastomosis) will be presented alongside its 95% Clopper-Pearson confidence interval.
- The biliary cannulation success rate (percentage of procedures with the ability to selectively cannulate the bile duct and conduct a cholangiography in relation to all cases with enteroscopy success) will be presented alongside its 95% Clopper-Pearson confidence interval.
- The therapeutic (procedural) success rate (percentage of procedures in which the intended treatment could be successfully completed after successful cannulation) will be presented alongside its 95% Clopper-Pearson confidence interval.
- The total procedure time (period in minutes needed to complete the procedure) will be summarized descriptively.
- The enteroscopy time will be summarized descriptively.
- The outcomes for the items in the user feedback for the judgement of handling characteristics and other aspects will be tabulated in frequency tables.

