11.1.8.1 Procedure with PowerSpiral - Categorical Parameters - SAF Reference: annCRF, Procedure with PowerSpiral, Procedural Information Parameters: categorical parameters Analyses: Absolute and relative frequencies	FT
11.1.8.2 Procedure with PowerSpiral - Continuous Parameters - SAF Reference: annCRF, Procedure with PowerSpiral, Procedural Information Parameters: Number of staff needed, length of procedure, time to reach papilla or biliary anastomosis, time scope out, enteroscopy duration, total procedure duration, total radiation dose Analyses: Descriptive statistics	DT
11.1.8.3 Therapeutic Interventions – Intervention Type - SAF Reference: annCRF, Therapeutic interventions during the procedure Parameters: Intervention type Analyses: Absolute and relative frequencies	FT
11.1.8.4 Therapeutic Interventions – Other Intervention - SAF Reference: annCRF, Therapeutic interventions during the procedure Parameters: Other intervention, please specify Analyses: Listing of free text	GL
11.1.8.5 Therapeutic Interventions – Continuous Parameters - SAF Reference: annCRF, Therapeutic interventions during the procedure Parameters: Number of stents, calculated duration Analyses: Descriptive statistics	DT
11.2.1 Assessment After Procedure - Categorical Parameters - ITT Reference: annCRF, Assessment after procedure Parameters: Intervention successful, therapeutic management plan modified during procedure Analyses: Absolute and relative frequencies	FT
11.2.2 Assessment After Procedure - Listing of Diagnoses - ITT Reference: annCRF, Assessment after procedure Parameters: Final diagnosis/assessment after ERCP Analyses: Listing of free text	GL
11.2.3 Evaluation of Procedure - Categorical Parameters - ITT Reference: annCRF, Evaluation Parameters: Handling, instrument insertion, precision, time needed, staff and resources needed Analyses: Absolute and relative frequencies by category (worse, similar, better)	FT

Description of table / figure / listing	Type
11.2.4 Evaluation of Procedure - Total Success Rate - ITT Reference: SAP section 3.6 Parameters: Total success rate Analyses: Absolute and relative frequencies, confidence interval	FT
11.2.5 Evaluation of Procedure - Total Enteroscopy Success Rate - ITT Reference: SAP section 3.6 Parameters: Total enteroscopy success rate Analyses: Absolute and relative frequencies, confidence interval	FT

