11.2.6 Evaluation of Procedure - Biliary Cannulation Success Rate - ITT Reference: SAP section 3.6 Parameters: Biliary cannulation success rate Analyses: Absolute and relative frequencies, confidence interval	FT
11.2.7 Evaluation of Procedure - Therapeutic (Procedural) Success Rate - ITT Reference: SAP section 3.6 Parameters: Therapeutic (procedural) success rate Analyses: Absolute and relative frequencies, confidence interval	FT
11.3.1.1 Adverse Events during procedure - SAF Reference: annCRF, (Serious) adverse events during procedure Parameters: Trigger question on AEs Analyses: Absolute and relative frequencies	FT
11.3.1.2.1 Adverse Events by category - SAF Reference: annCRF, Adverse event, Adverse event details Parameters: Adverse event category Analyses: Absolute and relative frequencies	FT
11.3.1.2.2 Serious Adverse Events by category - SAF Reference: annCRF, Adverse event, Adverse event details Parameters: Adverse event category Analyses: Absolute and relative frequencies	FT
11.3.1.3 Adverse Events by category - Listing of other AEs - SAF Reference: annCRF, Adverse event, Adverse event details Parameters: Free text Analyses: Listing of free text	GL
11.3.1.4.1 Adverse Events - Relatedness - SAF Reference: annCRF, Adverse event, Adverse event details Parameters: Relatedness Analyses: Absolute and relative frequencies	FT

Description of table / figure / listing	Type
11.3.1.4.2 Serious Adverse Events - Relatedness - SAF Reference: annCRF, Adverse event, Adverse event details Parameters: Relatedness Analyses: Absolute and relative frequencies	FT
11.3.1.5.1 Adverse Events - Seriousness - SAF Reference: annCRF, Adverse event details Parameters: Seriousness and seriousness components (e.g. death), outcome Analyses: Absolute and relative frequencies	FT
11.3.1.5.2 Adverse Events - Seriousness – SAF Reference: annCRF, Adverse event details Parameters: Seriousness and seriousness components Analyses: Listing of free text	GL
11.3.1.6.1 Adverse Events - Therapy - SAF Reference: annCRF, Adverse event details Parameters: Therapy Analyses: Absolute and relative frequencies	FT
11.3.1.6.2 Adverse Events - Listing of Therapy - SAF Reference: annCRF, Adverse event details Parameters: Other, please specify Analyses: Listing of free text	GL
11.3.1.7.1 Adverse Events - Relatedness - SAF Reference: annCRF, Adverse event details Parameters: Related to enteroscopy, ERCP, sedation, PowerSpiral device Analyses: Absolute and relative frequencies	FT

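### The SAP's ITT population is a per-protocol set, and all four success rates with intervals are planned on it alone

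*SAP*

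**What the plan says.** SAP 3.1 defines two sets. SAF is everyone with at least one enteroscopy. ITT is "all patients who underwent at least one enteroscopy and did not have any major protocol deviation". The exclusion is stated a second time in the same section, where efficacy is assigned to this set, so it is not a slip of wording.

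SAP 3.6 opens with "The following efficacy analyses will be performed based on the ITT population" and then lists the total, enteroscopy, cannulation and therapeutic success rates, each with a 95% Clopper-Pearson interval, followed by the two procedure times and the user feedback. The output list in SAP 3.9 matches for the rates, from "11.2.4 Evaluation of Procedure - Total Success Rate - ITT" through "11.2.7 Evaluation of Procedure - Therapeutic (Procedural) Success Rate - ITT". The post-procedure assessment ("11.2.1 Assessment After Procedure - Categorical Parameters - ITT"), which includes whether the intervention succeeded, and the user feedback ("11.2.3 Evaluation of Procedure - Categorical Parameters - ITT") are also on this set. SAP 3.8 plans no further analyses.

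Two places sit badly with this. SAP 2.4 and 3.6 define total success as "the number of therapeutic successes divided by the number of patients who received an enteroscopy", which read literally is the SAF denominator. The procedure times, which SAP 3.6 places on ITT, are tabulated in "11.1.8.2 Procedure with PowerSpiral - Continuous Parameters - SAF".

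Protocol section 7 names eligibility deviations as major but says the list is not limited to them. The clinical operations manager and the statistician classify deviations at the end of the study.

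**The concern.** A reader who sees a rate labelled ITT in a single-arm device study will assume that it covers every treated patient. Here it does not, and no planned table supplies the all-treated rate with its interval.

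Membership of the set is partly a matter of judgement. The list of major deviations is open, the study is open-label with one arm, and nothing in the documents keeps the two classifiers from seeing the success fields. If exclusion is related to success, the reported rates shift; if it is not, they stay put on average.

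There is no efficacy test (protocol 4.1.2), so no pass/fail decision is at stake. The estimates and their intervals are themselves the efficacy result, and protocol 3.2.3 intends to set Phase B results against balloon-assisted and manual-spiral reference data. The denominator and its label therefore matter.

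**Working it through.** **Comparing the definitions.** SAF is all treated patients. The SAP's ITT is SAF minus treated patients with a major deviation. The only difference between the two sets is adherence to the protocol, which is what defines a per-protocol set. Going through SAP 3.9, tables 11.2.1 to 11.2.7 are all marked ITT, and no table gives a success rate with an interval on SAF or on all enrolled patients.

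**No planned figure to reproduce.** Protocol 3.3.6 sets 100 patients on clinical reasoning, without an expected rate or a precision target. What follows is an illustration. The documents give the target of 100 and the interval method. The number of successes and the number excluded are assumptions.

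**Formulas.** Let N be the number treated, x the successes and k the number excluded.
- All treated: x/N.
- All k excluded are successes: (x − k)/(N − k).
- All k excluded are failures: x/(N − k).
- Distance between these two extremes: k/(N − k).

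Intervals are exact two-sided 95% Clopper-Pearson.

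**N = 100, x = 70.** All treated: 70/100 = 70.0% (60.0 to 78.8).

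| k | all excluded are successes | all excluded are failures | k/(N − k), points |
|---|---|---|---|
| 2 | 68/98 = 69.4% (59.3 to 78.3) | 70/98 = 71.4% (61.4 to 80.1) | 2.0 |
| 5 | 65/95 = 68.4% (58.1 to 77.6) | 70/95 = 73.7% (63.6 to 82.2) | 5.3 |
| 10 | 60/90 = 66.7% (55.9 to 76.3) | 70/90 = 77.8% (67.8 to 85.9) | 11.1 |

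The largest shifts from 70.0% are +1.4 and −0.6 points for k = 2, +3.7 and −1.6 for k = 5, and +7.8 and −3.3 for k = 10. If 10 patients are excluded at the average failure rate (3 failures, 7 successes), the result is 63/90 = 70.0% (59.4 to 79.2): no shift, and a slightly wider interval.

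**N = 100, x = 80.** All treated: 80.0% (70.8 to 87.3). The extremes are 79.6% to 81.6% for k = 2, 78.9% to 84.2% for k = 5, and 77.8% to 88.9% for k = 10.

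**Scope of these ranges.** They apply to total success and, with x read as successful enteroscopies, to enteroscopy success, because both divide by treated patients. Under SAP 2.4, cannulation success divides by successful enteroscopies and therapeutic success by successful cannulations. Excluding a patient whose enteroscopy failed leaves both unchanged. For these two rates, N and k must be replaced by the conditional denominator and the number excluded from it.

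**Timing.** Protocol section 16 puts database lock and the data review meeting in February 2023 and the analysis in April 2023. Classification before analysis is the right order. What is absent is a closed list of excluding deviations and any restriction on seeing the success fields.

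**The case against.** The best case for the plan is that the practical effect may be small and much of it would be visible. The only deviation named as major concerns eligibility, which is settled before the procedure. Entry criteria are broad (protocol 1.2), and the registry adds nothing to routine care, so there are few other ways to deviate. Protocol 3.3.5 defines study end as database lock, which places classification before the analysis. Table 11.1.2 will show how many patients are in each set, and table 11.1.3 tabulates eligibility on SAF. Every listing carries the analysis population, so listings 11.5.1, 11.5.9 and 11.6.1 would let a reader rebuild some counts. The denominator wording can be read as applying within the ITT set. The stated objective concerns use as intended by the manufacturer, which gives some reason to look at patients without major deviations.

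Much of this stands as a limit on size. Nothing in the documents supports 5 or 10 exclusions that all failed, and with 2 exclusions the shift is small beside the interval. The denominator point is an ambiguity, not a proven contradiction. None of it repairs the label or supplies an all-treated rate with its interval. A listing is not a planned estimate, and none of the outputs is described as giving the reason for an exclusion on grounds other than eligibility. The trial summary states the purpose as performance in daily medical practice, which favours the all-treated set as the main one.

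**Conclusion.** The concern holds. The set called ITT in SAP 3.1 is a per-protocol set, and all four success rates with intervals are planned on it alone. Following the SAP as written would give mislabelled rates that omit treated patients under an open-ended classification.

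The size is unknown. Under the assumed 70 successes in 100 treated, the total success rate could move by at most +1.4 or −0.6 points with 2 exclusions and +7.8 or −3.3 with 10. It would not move on average if exclusion is unrelated to success. The documents do not indicate a direction. Because Phase B is exploratory without an efficacy test, the effect is confined to the estimates, their label and their comparison with reference data. This should be fixed before the analysis, but it does not undermine the study. The mismatch of sets for the procedure times is real and minor.

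**What to change.** In the SAP:

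1. Make SAF the main set for tables 11.2.1 to 11.2.7, and state SAF for the two procedure times in 3.6 so that they agree with table 11.1.8.2. State the set for the subgroup analyses in 3.3 as well, since none is given.
2. Rename the present ITT set per-protocol in 3.1, 3.6 and table 11.1.2, and report the four success rates on it as a sensitivity analysis.
3. List in advance the deviations that exclude a patient from the per-protocol set, including the eligibility deviation named in protocol section 7. Classify them without reference to the success fields at the data review already scheduled before the analysis. Protocol section 7 can stay as it is; the SAP list only decides membership of the sensitivity set.
4. Add a listing of each major deviation with its reason.

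Items 1 and 2 correct the error. Items 3 and 4 make the sensitivity set reproducible.

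The cost is edits to SAP 3.1, 3.3, 3.6 and 3.9: a change of set in seven existing tables, one relabelled table, four additional sensitivity tables and one listing. SAF already exists, no new data are needed, and the timeline does not change. The main rates may turn out less favourable than on the restricted set, or more so.
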